2.2.1 Blinatumomab in Precursor B-cell Acute Lymphoblastic Leukemia

A large, 189 patient phase II study in precursor B cell acute lymphoblastic leukemia (B-ALL), confirmed the safety and efficacy of blinatumomab and was the basis for FDA approval in that disease. Blinatumomab was given as a continuous IV infusion (4 weeks on followed by 2 weeks off) for up to 5 cycles (cycle 1 only: 9 μ g/d days 1-7; then 28 μ g/d). Regardless of causality, the most common adverse events (AEs) were pyrexia (59%), headache (35%) and febrile neutropenia (29%). The most common grade ≥ 3 AEs were febrile neutropenia (26%), anemia (15%) and neutropenia (15%); 2% had grade ≥ 3 cytokine release syndrome. The most common grade ≥ 3 nervous system disorders were headache (4%), encephalopathy (3%) and ataxia (2%). Three (2%) pts had grade 5 AEs considered treatment-related (sepsis, n=2; candida infection, n=1).¹⁶

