14.0. STATISTICAL CONSIDERATIONS

The cohort of 9 patients already treated demonstrates the feasibility and safety of blinatumomab as a single agent for the treatment of RT. The overall toxicity profile of blinatumomab in RT was very favorable and this cohort of patients can be used as a “safety cohort,” prior to proceeding with a phase II study evaluating the combination with ibrutinib + nivolumab. As discussed above, the combination of ibrutinib and nivolumab was also very well tolerated.

We have completed a phase II study of ibrutinib + nivolumab, and achieved an ORR of 43%. This will serve as our “base case” estimation of the response rate that we would see with the combination of ibrutinib + nivolumab. If blinatumomab (ORR 1/8 = 12.5%) provides additive benefit only, this will result in an ORR of 50-55% with the combination of ibrutinib + nivolumab and blinatumomab. However, we expect synergy between the two regimens. We have therefore designed our statistical analysis around achieving an ORR of approximately 60%, which would suggest some synergy

between the two regimens. Higher response rates would suggest a greater degree of synergy between blinatumomab and ibrutinib + nivolumab, which we hope to achieve.

We propose to enroll an additional 21 patients, with the goal of evaluating the efficacy and safety of the proposed combination therapy. A sample size of 21 patients ensures that, if the trial is not terminated early, a posterior 90% credibility interval for overall response rate will have width of 0.33, under the assumption of a 60% of overall response rate (13/21 responses) and beta prior as described below. Under this scenario, the lower boundary of the 90% credibility interval matches the 43% ORR that was seen with ibrutinib + nivolumab therapy.

The primary outcome will be overall response (ORR), assessed after completion of 2 courses of blinatumomab.

We will utilize a Bayesian trial design to enable simultaneous monitoring of efficacy and toxicity using the approach of Thall, Simon, and Estey (1995, 1996). After an initial 6 patient safety cohort, subsequent patients will be enrolled in cohorts of size 3.

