The existing trial of blinatumomab as a single agent assumes that a toxicity rate greater than 31% would be excessive. Since we propose combining blinatumomab with two additional agents, we aim to achieve a higher ORR, and allow for acceptable toxicity no higher than 40%. For the purposes of toxicity monitoring, toxicity will be defined as follows: grade 4-5 neurotoxicity or CRS; grade 3 neurotoxicity or CRS that fails to resolve within 1 week or recurs at grade ≥ 3 severity on re-challenge; grade 3-5 therapy-related immune-related toxicity at least possibly related to nivolumab.

For the Bayesian design, the following parameter settings will be used:

- For the standard treatment response and toxicity rates, constant rates of 0.4 are assumed.
- For the response and toxicity rates under the proposed treatment, a beta(0.8, 1.2) prior is assumed for each rate, which has the same mean as the rates under the standard treatment, and an effective sample size of 2.
- The maximum number of patients if no early stopping is applied will be 21, and a minimum of 6 patients will be treated before stopping.
- The planned cohort size is 3.

- The trial will be stopped early based on response if the posterior probability that the response rate of the experimental treatment is less than the current standard rate is greater than 0.9.
- The trial will be stopped early based on toxicity if the posterior probability that the toxicity rate of the experimental treatment is greater than the current standard rate is greater than 0.8.
- Toxicity will be monitored continuously for the first year of treatment.

Response Stopping Boundaries

# Patients (in complete cohorts of 3) (inclusive)	Stop the trial if there are this many responses total:

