	# Toxicities (inclusive)
3	Never stop with this many patients
6	4-6
9	5-9
12	7-12
15	8-15
18	10-18
21	Always stop with this many patients

Summary of operating characteristics

The operating characteristics are summarized in the table below. The probabilities of stopping the trial early are exact calculations from MultcLean Desktop under the assumption that response is independent of toxicity.

True Toxicity Rate	True OR Rate	Prob(stop the trial early)	Avg # patients enrolled (25 th – 75 th percentile)
0.2	0.6	0.04	20.5 (21 – 21)
	0.5	0.07	20.1 (21 – 21)
	0.4	0.19	19.0 (21 – 21)
	0.3	0.45	16.4 (12 – 21)
0.3	0.6	0.14	19.2 (21 – 21)
	0.5	0.17	18.8 (21 – 21)
	0.4	0.28	17.8 (15 – 21)
	0.3	0.51	15.5 (9 – 21)
0.4	0.6	0.36	16.4 (9 – 21)
	0.5	0.39	16.2 (9 – 21)
	0.4	0.46	15.4 (9 – 21)
	0.3	0.63	13.6 (6 – 21)
0.5	0.6	0.64	12.9 (6 – 21)
	0.5	0.66	12.7 (6 – 15)
	0.4	0.70	12.2 (6 – 21)
	0.3	0.79	11.1 (6 – 15)

Analysis Plan

Summary statistics will be provided for continuous variables. Frequency tables will be used to summarize categorical variables. Logistic regression will be utilized to assess the effect of patient prognostic factors on the response rate and the toxicity rate. The distribution of time-to-event endpoints will be estimated using the method of Kaplan and Meier. Cox proportional hazard regression will be employed for multivariate analysis on time-to-event outcomes.

An Efficacy/Safety Summary will be submitted to the IND Office Medical Monitor, after the first 6 evaluable patients complete 8 weeks of study treatment, and every 3 evaluable patients thereafter. Toxicity information of previously submitted patients will be updated during every submission.

Trial Conduct

Conducting a trial designed by this method does not require software since the stopping conditions have been tabulated before the trial begins.

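### The plan requires no review before the next enrolment after a treatment-related death, and its one toxicity rule does not separate deaths from non-fatal events

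*Combined protocol and SAP*

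**What the plan says.** Section 14.0 defines a single yes/no toxicity for monitoring. It comprises grade 4-5 neurotoxicity or CRS, grade 3 neurotoxicity or CRS that persists beyond a week or recurs on re-challenge, and "grade 3-5 therapy-related immune-related toxicity at least possibly related to nivolumab". The plan will "allow for acceptable toxicity no higher than 40" per cent. It stops for toxicity when the posterior probability that the rate exceeds 0.4 is above 0.8, with a beta(0.8, 1.2) prior.

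Timing is restricted: "a minimum of 6 patients will be treated before stopping". The toxicity table's entry at 3 patients is "Never stop with this many patients", and the first active boundary is 4 toxicities in 6. At 6 patients the response table stops only for 0 responses.

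Other provisions bear on early safety:

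- Section 14.0: "After an initial 6 patient safety cohort, subsequent patients will be enrolled in cohorts of size 3".
- Section 14.0: "Toxicity will be monitored continuously for the first year of treatment".
- Section 14.0, Analysis Plan: "An Efficacy/Safety Summary will be submitted to the IND Office Medical Monitor, after the first 6 evaluable patients complete 8 weeks of study treatment", and then after every 3 further evaluable patients.
- Section 11.2: a written report to the IND Office by the next working day for life-threatening or fatal events that are both unexpected and related.
- Section 11.3: all serious adverse events go to the IND Office within 5 working days, with onward reporting to the FDA and the IRB.
- Section 11.5: serious adverse events go to BMS within 24 hours or one business day.

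**The concern.** The regimen adds a T-cell engager to a PD-1 inhibitor and ibrutinib. Section 6.1.4 itself warns that nivolumab may potentiate blinatumomab's adverse events. Section 14.0 describes the component regimens as well tolerated, but the triplet is what the 6-patient safety cohort is there to test. A related death in that cohort is the event most likely to call for a decision before anyone else is treated.

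The written rule does not provide that decision, for three reasons:

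- A death carries the same weight as a grade 3 immune event and is judged against a 40% limit.
- Before 6 patients the rule cannot act at all.
- Some deaths are never counted. In the 189-patient leukemia study in section 2.2.1, "Three (2%) pts had grade 5 AEs considered treatment-related", and all three were infections. Sections 5.3.5.1, 5.3.5.2 and 5.3.5.5 describe fatal bleeding, arrhythmia and infection with ibrutinib. Unless such a death is immune-related, it leaves the toxicity count unchanged.

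The surrounding provisions report or summarise; none holds enrolment. The first summary waits for 6 evaluable patients to complete 8 weeks. The plan does not define evaluable, and a patient who dies early cannot complete 8 weeks. Blinatumomab starts only on day 15 (section 4.3), and no stagger within the first 6 patients is stated.

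**Working it through.** **Inputs (section 14.0).** Prior beta(0.8, 1.2) for each rate; reference rate 0.4; cutoffs 0.8 (toxicity) and 0.9 (response); looks at 6, 9, 12, 15 and 18 patients; maximum 21.

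**Reproducing the plan.** With x events in n patients the posterior is beta(0.8 + x, 1.2 + n − x). This returns the tabulated toxicity boundaries (4/6, 5/9, 7/12, 8/15, 10/18) and response boundaries (0/6, 1/9, 2/12, 3/15, 4/18). An exact recursion over the looks, with response independent of toxicity, returns all 16 early-stopping probabilities. For example, toxicity 0.2 with response 0.6 gives 0.037 (stated 0.04), and 0.4 with 0.4 gives 0.462 (stated 0.46). The tables therefore match their stated parameters.

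**What the rule does with related deaths of the counted types.**

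| Counted toxicities / patients | Posterior | Pr(rate > 0.4) | Written rule |
|---|---|---|---|
| 1/3 | beta(1.8, 3.2) | 0.396 | cannot act |
| 3/3 | beta(3.8, 1.2) | 0.958 | cannot act, although above 0.8 |
| 1/6 | beta(1.8, 6.2) | 0.121 | continue |
| 2/6 | beta(2.8, 5.2) | 0.361 | continue |
| 3/6 | beta(3.8, 4.2) | 0.657 | continue |
| 4/6 | beta(4.8, 3.2) | 0.875 | stop |

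Three deaths in 6 therefore continue only if none of the other three patients has a counted toxicity and at least one of the 6 responds. For response, 0/6 gives Pr(rate < 0.4) = 0.983 and stops; 1/6 gives 0.879 and does not. If each of the other three patients has an assumed 10%, 20% or 30% chance of a counted toxicity, a fourth event brings the stop with probability 1 − (1 − q)³ = 0.271, 0.488 or 0.657.

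**How likely these cases are.** The documents give no related-death rate for this triplet in Richter transformation. I use d = 2% (3/189 = 1.6%, which the protocol rounds to 2%; single agent, different disease) and assumed values of 5% and 10%.

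| d | 3 of first 3: d³ | ≥3 of 6 | ≥2 of 6 | ≥1 of 6: 1 − (1 − d)⁶ |
|---|---|---|---|---|
| 2% | 0.000008 | 0.0002 | 0.006 | 0.11 |
| 5% | 0.0001 | 0.002 | 0.033 | 0.26 |
| 10% | 0.001 | 0.016 | 0.114 | 0.47 |

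**Whole trial.** If all these deaths are counted and a further 10% of patients have a non-fatal counted toxicity (assumed), the total rates are 12%, 15% and 20%. The toxicity boundary then stops the trial with probability 0.004, 0.009 and 0.029. At such death rates the boundary is almost never what prompts action.

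**The case against.** The strongest reply is that the boundary is not the only way to stop. Nothing in section 14.0 says it is. Toxicity is watched continuously, fatal events reach the IND Office, IRB, FDA and BMS, and any responsible party could halt the trial. This stands. A reader might infer from the table that three deaths in the first three patients could not stop the trial. The documents do not support that; those deaths cannot trigger the tabulated boundary, which is a narrower statement. It is also a remote case, at 0.001 or less for death rates up to 10%. Nor do the documents give any ground for testing the rule at much higher death rates.

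Second, a 6-patient safety cohort, boundaries at complete cohorts and a Medical Monitor summary can be read as staged enrolment. That is a fair reading of intent, but no wait is stated within or between cohorts, and the summary schedule is not linked to a death.

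Third, early risk is limited clinically. Blinatumomab begins at 9 mcg/day with 17 inpatient days, and grade 4 CRS or neurotoxicity ends it permanently. These measures protect the individual patient; they do not govern enrolment of the next one.

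Fourth, the IRB policy cited in section 11.3 may prescribe a step after a death. It was not available, nor were the title page and part of the background section. The finding covers the available text only.

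Fifth, the 6-patient minimum and the 40% limit are disclosed design choices, and the tables contain no error. That is correct, and neither needs to change.

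**Conclusion.** The concern holds as a gap in the written plan. The only toxicity rule pools deaths with non-fatal events, cannot act before 6 patients, and does not count related deaths outside three categories. No available text requires a review before the next enrolment after a related death. The 3/3 and 3/6 cases show the limit of the rule and are unlikely. The practical gap follows a first related death, which occurs in the first 6 patients with probability 0.11, 0.26 or 0.47 at rates of 2%, 5% or 10%. These figures assume independent patients and a constant rate; the 2% is borrowed from another disease and a single agent, and the 5% and 10% are assumptions. The change is worth making because it is cheap and the event is serious. It does not call the boundaries or the sample size into question.

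**What to change.** Keep the pooled boundary and add one sentence to section 14.0:

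> Accrual pauses after any grade 5 event at least possibly related to study treatment (not due to disease progression), including within the first 6 patients, until the IND Office Medical Monitor has promptly reviewed it and documented a decision to continue, amend or stop.

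This reaches related deaths outside the pooled definition, such as fatal infection, bleeding or arrhythmia. It guarantees a documented review, not a stop. It uses the existing Medical Monitor and the serious adverse event reports already sent to the IND Office, and leaves the boundaries and the operating-characteristics table as they are.

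The cost is interrupted accrual. Over 21 patients the expected number of pauses is 21 × d = 0.42, 1.05 or 2.10 at related-death rates of 2%, 5% or 10%, and the chance of at least one, 1 − (1 − d)²¹, is 0.35, 0.66 or 0.89. Attribution will often be uncertain in a disease with median survival under a year in most series (section 2.1). The exclusion for disease progression and the requirement for prompt review are there to keep pauses few and short.

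### Should the futility rule test response against 43%, the ibrutinib + nivolumab base case, instead of 0.40?

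*Combined protocol and SAP*

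**What the plan says.** All the material is in Section 14.0 (Statistical Considerations).

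- **Base case.** "We have completed a phase II study of ibrutinib + nivolumab, and achieved an ORR of 43" per cent. The plan calls this its "estimation of the response rate that we would see with the combination of ibrutinib + nivolumab".
- **Interval reference.** With 21 patients and 13 responses, "a posterior 90% credibility interval for overall response rate will have width of 0.33", and "the lower boundary of the 90% credibility interval matches the 43% ORR that was seen with ibrutinib + nivolumab therapy".
- **Monitoring constant.** "For the standard treatment response and toxicity rates, constant rates of 0.4 are assumed". Each rate has a beta(0.8, 1.2) prior, "which has the same mean as the rates under the standard treatment, and an effective sample size of 2".
- **Futility rule.** The trial stops if the posterior probability that "the response rate of the experimental treatment is less than the current standard rate is greater than 0.9".
- **Reason for 40%.** With three drugs, "we aim to achieve a higher ORR, and allow for acceptable toxicity no higher than 40" per cent. This explains the toxicity figure. The available text has no matching sentence for response.
- **Operating characteristics.** At true toxicity 0.5 and true response 0.5, the table gives an early-stopping probability of 0.66, a mean of 12.7 patients and quartiles of 6 and 15.

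**The concern.** The plan reasons about benefit from 43% but stops for lack of benefit against 0.40. Response and toxicity share one parameter line and one prior, so the response figure could have been carried over from the toxicity ceiling.

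The standard rate fixes the cut-offs, and the trial is run from the printed table without software. Too low a constant lets a poor triplet enrol longer. For example, 5 responses in 18 patients continues under the printed rule but would stop at a constant of 0.43, although the most it can still reach is 8/21 = 38%.

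The quartile is a separate matter. If only 66% of trials stop early, 34% run to 21 patients, and a 75th percentile of 15 is impossible.

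**Working it through.** **Inputs (Section 14.0).** Looks at n = 6, 9, 12, 15 and 18; maximum 21. Prior mean equal to the standard rate p0 with effective sample size 2, so Beta(a, b) with a = 2·p0 and b = 2·(1 − p0). Stop for futility if Pr(rate < p0) > 0.9. Stop for toxicity if Pr(rate > 0.40) > 0.8. Response and toxicity are taken as independent, as the plan states.

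**Formula.** With x responses in n patients the posterior is Beta(a + x, b + n − x). The rule stops when its distribution function at p0 exceeds 0.9. Operating characteristics come from exact enumeration over the five looks.

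**1. The plan's own figures, p0 = 0.40, Beta(0.8, 1.2).**
- At n = 18, x = 4 gives Beta(4.8, 15.2) and probability 0.943 (stop). x = 5 gives Beta(5.8, 14.2) and 0.860 (continue). The printed 0-4 is right.
- All five response cut-offs (0, 1, 2, 3, 4) and all five toxicity cut-offs (4, 5, 7, 8, 10) reproduce.
- All 16 stopping probabilities and all 16 means reproduce to rounding.
- 13/21 gives Beta(13.8, 9.2), with a 90% interval of 0.430 to 0.760 and width 0.329. Both interval statements hold.

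**2. Replacing 0.40 by 43%.** The unrounded rate is not in the documents. A figure of 43% covers 0.425 to 0.435, and 3/7 is an assumed value inside that range. The futility columns use the response rule alone. Mean N is at toxicity 0.2 and response 0.30, with both rules applied.

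| p0 | Prior | Cut-offs at 6, 9, 12, 15, 18 | Futility stop, true rate 0.30 | 0.43 | 0.60 | Mean N |
|---|---|---|---|---|---|---|
| 0.40 (plan) | Beta(0.80, 1.20) | 0, 1, 2, 3, 4 | 0.429 | 0.116 | 0.009 | 16.4 |
| 0.425 | Beta(0.85, 1.15) | 0, 1, 2, 3, 4 | 0.429 | 0.116 | 0.009 | 16.4 |
| 3/7 | Beta(0.857, 1.143) | 0, 1, 2, 3, 5 | 0.566 | 0.173 | 0.012 | 16.0 |
| 0.43 | Beta(0.86, 1.14) | 0, 1, 2, 4, 5 | 0.602 | 0.201 | 0.015 | 15.4 |
| 0.435 | Beta(0.87, 1.13) | 1, 1, 3, 4, 5 | 0.678 | 0.298 | 0.051 | 12.6 |
| 0.43 | Beta(0.80, 1.20), as printed | 1, 2, 3, 4, 5 | 0.691 | 0.315 | 0.056 | 12.15 |

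The number of changed cut-offs is 0, 1, 2, 4 or 5. At 0.43 with the re-centred prior, the n = 15 cut-off moves because 4/15 gives 0.9005, which is 0.0005 over the threshold. The n = 6 cut-off stays because 1/6 gives 0.8994, which is 0.0006 under it.

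At a true rate of 0.50, the lower end of the plan's additive-benefit range, futility stopping is 4.5% now. It would be 8.3% at 0.43 with the re-centred prior and 17.0% with the printed prior.

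**3. The 5/18 example.** The posterior probability is 0.860 at 0.40, 0.904 at 3/7 and 0.906 at 0.43. The best finish, (5 + 3)/21 = 0.381, lies below 0.40 as well as below 0.43. Continuing there therefore reflects the 0.9 threshold too, not only the choice of constant.

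**4. The quartile.** At toxicity 0.5 and response 0.5, the cumulative stopping probability is 0.354 (n = 6), 0.542 (9), 0.572 (12), 0.642 (15) and 0.656 (18). The first size at which it reaches 0.75 is 21. The printed 0.66 and 12.7 are correct, and so are the other 31 quartile entries. The next row, with stopping probability 0.70, correctly shows 6 and 21.

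**The case for a change.** The strongest case for a change is this. A triplet no better than the doublet's 43% stops for futility in only 12% of trials, against 20% with 0.43 and a re-centred prior, or 31% with the printed prior. At a true rate of 0.30 the printed rule stops 43% of trials, against 60% or 69%. With the re-centred prior the price at the 60% target is small, 0.9% rising to 1.5%. The n = 18 cut-off moves under either prior. The plan itself makes 43% its reference, so using that figure in the rule needs no new judgement.

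Part of this stands: the difference is real, and the available text gives no reason for 0.40 as a response rate.

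The rest does not amount to a fault. The figure of 43% is the expected rate for the backbone and the yardstick for the final interval; 0.40 is the constant for stopping early. No sentence says that the two must be equal. An interim futility rule exists to catch clearly poor results, and even with 0.43 and a re-centred prior about 80% of trials at a true 43% pass every futility look. The versions that stop substantially earlier at a true rate of 0.30 (mean 12.6 or 12.15 patients) also raise wrongful stopping at 0.60 to 5.1% or 5.6%.

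**Conclusion.** No change to the plan is called for. The use of 0.40 is a fair trade-off that the text leaves unexplained: a slightly lenient futility constant, applied correctly throughout. The later part of the Section 2 background, to which Section 14.0 appears to refer back, was not available to this review and may give the reason.

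Aligning the rule with 43% would save 0.4 to 1.0 patient on average at toxicity 0.2 and response 0.30 (3/7 or 0.43, re-centred prior), in exchange for more stopping of a regimen with moderate benefit. The replacement boundaries would rest on decimals that the documents do not give and on a choice of prior. There is no formal end-of-trial test for the constant to distort. The final interval hardly depends on it: 0.430 to 0.760 with the printed prior, 0.433 to 0.762 with Beta(0.86, 1.14).

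The quartile is certainly wrong, and 21 should be read for 15. It is a clerical slip beside a correct stopping probability and mean, and it touches no boundary, decision or conclusion.

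These results assume looks at complete cohorts and independence of response and toxicity, as the plan does. The range 0.425 to 0.435 and the value 3/7 are assumptions about the unrounded rate.

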	# Responses (inclusive)
3	Never stop with this many patients
6	0
9	0-1
12	0-2
15	0-3
18	0-4
21	Always stop with this many patients

Stopping boundaries for toxicity

# Patients (in complete cohorts of 3) (inclusive)	Stop the trial if there are this many toxicities total:

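### The toxicity rule can call for 1 or 2 more patients after the stop is already certain; a running ceiling for toxicity would avoid this without changing any published stopping probability

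*Combined protocol and SAP*

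**What the plan says.** Section 14.0 (Statistical Considerations) sets the enrolment pattern: "After an initial 6 patient safety cohort, subsequent patients will be enrolled in cohorts of size 3". Its parameter list caps the trial at 21 patients and adds "a minimum of 6 patients will be treated before stopping" and "The planned cohort size is 3". The trial stops for toxicity when the posterior probability that the toxicity rate exceeds the fixed reference of 0.4 is above 0.8, under a beta(0.8, 1.2) prior.

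The table of toxicity stopping boundaries is indexed by "Patients (in complete cohorts of 3) (inclusive". For 3 patients it says "Never stop with this many patients". It then stops at 4 or more toxicities in 6 patients, 5 in 9, 7 in 12, 8 in 15 and 10 in 18. There is no row for 4, 5, 7, 8 or any other incomplete cohort. The closing Trial Conduct paragraph treats the tabulated conditions as all that is needed to run the trial, and summaries go to the medical monitor after 6 evaluable patients and then after every 3.

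The same parameter list also says "Toxicity will be monitored continuously for the first year of treatment". It does not say what this monitoring triggers between two rows of the table.

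**The concern.** A count of patients with toxicity can only rise. Once it reaches the boundary of the next look, the decision at that look is settled, and patients enrolled in between cannot alter it. The 6-patient minimum is explicit, so after 4 toxicities among the first 4 or 5 patients the text still calls for the rest of the six to be treated. In later cohorts the table points the same way, while the sentence on continuous monitoring leaves room for an earlier halt.

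At stake is exposure with no bearing on the decision. The counted events include grade 4-5 neurotoxicity and CRS, grade 3 forms that persist or recur, and grade 3-5 immune toxicity at least possibly related to nivolumab.

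**Working it through.** **Inputs (all Section 14.0).** Reference rates: "For the standard treatment response and toxicity rates, constant rates of 0.4 are assumed". Prior beta(0.8, 1.2) for each rate. Toxicity threshold 0.8, response threshold 0.9. Looks at 6, 9, 12, 15 and 18. Response and toxicity independent.

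**Step 1: reproduce the toxicity boundaries.** With x toxicities in n patients, compute Pr(p > 0.4) under Beta(0.8 + x, 1.2 + n − x). The boundary is the smallest x giving more than 0.8.

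| n | one below the boundary | at the boundary |
|---|---|---|
| 6 | 3: 0.657 | 4: 0.875 |
| 9 | 4: 0.58 | 5: 0.8005 |
| 12 | 6: 0.736 | 7: 0.882 |
| 15 | 7: 0.681 | 8: 0.834 |
| 18 | 9: 0.788 | 10: 0.896 |

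All five match the plan.

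**Step 2: reproduce the operating characteristics.** An exact recursion over (toxicities, responses), stopping only at the five looks, gives all 16 published stopping probabilities and average sample sizes to rounding. For example, toxicity 0.5 with response 0.6 gives 0.643 and 12.87 (published 0.64 and 12.9). So the design as evaluated does wait for 6 patients and then for complete cohorts.

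**Step 3: where can the stop be certain before its look?** Take outcomes as known in enrolment order.

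- Look at 6 (needs 4): possible at patient 4 (4 of 4) or patient 5 (4 of 5), leaving 2 or 1 patients.
- Look at 9 (needs 5): a running trial has at most 3 at patient 6, so 2 more are needed; possible at patient 8, leaving 1.
- Look at 12 (needs 7): at most 4 at patient 9, so 3 of 3 are needed; not possible early.
- Look at 15 (needs 8): at most 6 at patient 12, so 2 more are needed; possible at patient 14, leaving 1.
- Look at 18 (needs 10): at most 7 at patient 15, so 3 of 3 are needed; not possible early.

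At these points the plan's own criterion is already met: 0.983 (4 of 4), 0.942 (4 of 5), 0.875 (5 of 8) and 0.886 (8 of 14).

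**Step 4: how often (response rate 0.6).** The first two columns are p⁴ and 4p⁴(1 − p). The next two come from the recursion.

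| True toxicity | patient 4 | patient 5 | patient 8 | patient 14 | total |
|---|---|---|---|---|---|
| 0.2 | 0.0016 | 0.0051 | 0.0033 | 0.0003 | 1.0% |
| 0.3 | 0.0081 | 0.0227 | 0.0166 | 0.0032 | 5.1% |
| 0.4 | 0.0256 | 0.0614 | 0.0441 | 0.0127 | 14.4% |
| 0.5 | 0.0625 | 0.1250 | 0.0778 | 0.0253 | 29.1% |

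**Step 5: patients spared.** Multiply each column by the patients left (2, 1, 1, 1). At toxicity 0.5 this is 2 × 0.0625 + 0.1250 + 0.0778 + 0.0253 = 0.353, so mean enrolment falls from 12.87 to 12.51. At 0.2, 0.3 and 0.4 it falls from 20.51 to 20.49, 19.16 to 19.10 and 16.45 to 16.28.

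**Step 6: stopping probabilities.** A path that reaches the count early is still at or above it at the look, and no response look falls in between. The same paths therefore stop under either rule. The recursion confirms this for all 16 scenarios.

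**The case against.** The strongest reply is that nothing obliges the sponsor to fill a later cohort. Toxicity is to be monitored continuously, the 0.8 criterion is stated without a cohort limit, and Section 11.5 mentions that the sponsor or the nivolumab manufacturer may end or temporarily halt a study for safety reasons. This stands for patients 7 onward: the plan is ambiguous there. It does not stand for the first six, where the minimum is explicit.

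A reader might infer a stronger point, that patients must be treated needlessly in every cohort. The documents do not support it. Beyond the wording, Step 3 shows that early certainty cannot arise before the looks at 12 or 18. Nor can 5 toxicities be reached by patient 7, because a trial that continues past 6 has at most 3. Late toxicities in earlier patients could raise the count at other points, but the documents give no onset or accrual figures to size that.

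A second reply is that the saving is idealised. Blinatumomab starts on day 15 of cycle 1 (Section 4.3), and some counted events need a week without resolution or a recurrence on re-challenge. Patients 5 and 6 may already be on treatment when the fourth event is classified. This stands, and makes the figures an upper bound.

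A reader might also infer that 3 toxicities in 3 patients should stop the trial, since the posterior is then 0.958. But the 6-patient safety cohort and minimum are deliberate, and adding that row changes the design: it adds up to 0.0075 to the probability of stopping at response rate 0.6 and toxicity 0.2 to 0.4. It is not part of this point.

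**Conclusion.** The concern holds in limited form. The 6-patient minimum calls for 2 or 1 more patients after 4 toxicities in the first 4 or 5, when the stop is already certain. On the table reading, one further patient is treated at 8 or at 14. Across the plan's own toxicity range this affects 1.0% to 29.1% of trials at response rate 0.6, at most 2 patients in any trial, and 0.01 to 0.35 patients on average. At or below the 40% toxicity the plan calls acceptable, the average is no more than 0.17.

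These sizes assume that each outcome is known before the next patient starts, that toxicities are counted in enrolment order, and that response and toxicity are independent, as in the plan's table. The gain is small. The change is still worth making because it leaves the stopping probabilities intact and settles what continuous monitoring means.

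**What to change.** Reconcile the 6-patient minimum, the complete-cohort table and the continuous-monitoring sentence by adding one statement to Section 14.0. For toxicity only, each table row is a running ceiling: enrolment stops as soon as 4 toxicities are recorded within the first 6 patients, 5 within 9, 7 within 12, 8 within 15 or 10 within 18, without filling the cohort or reaching the 6-patient minimum. Keep the minimum and the complete cohorts for the response rule. The statement governs enrolment, not the care of patients already on treatment.

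The cost is that sentence and a recalculated average-N column with its percentiles. All 16 stopping probabilities stand.

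Applying the 0.8 criterion afresh after every patient is a different change and should not be adopted by default. With no 6-patient floor it would raise the stopping probability at response rate 0.6 from 0.04 to 0.08, 0.14 to 0.22 and 0.36 to 0.47 at toxicity 0.2, 0.3 and 0.4.
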